Patients in the CM plus stepped care arm who have PEth > 8 ng/ml at 3 months will progress to Step 2 and receive onsite treatment from an Addiction Psychiatrist (APM) and MET from the Social Worker in the HIV clinic. APM will provide care that is typically provided by physicians in specialty referral programs. We have used this model successfully in earlier trials.^{35,67} After an initial 45-minute evaluation session, the physicians will administer APM weekly for 2 weeks, every 2 weeks for 4 weeks and then monthly. The physician will 1) assess the impact of alcohol use on medical, psychiatric, social, employment, and legal functioning, 2) educate the patient about alcohol, 3) prescribe alcohol pharmacotherapy if indicated, 4) encourage abstinence and adherence to medication (as appropriate); 5) encourage lifestyle changes, avoidance of triggers and attendance at mutual-help groups; 6) identify and address medical complications of alcohol use; and 7) refer patients to indicated treatment services (e.g., vocational, housing or social service). Medications are useful adjuncts to counseling in initiating abstinence and preventing relapse in patients with AUD. Disulfiram, oral naltrexone, injectable naltrexone, and acamprosate are available at the seven sites. Naltrexone has the best evidence of efficacy and⁶⁸ we have demonstrated the safety of naltrexone in HIV-infected patients.⁶⁹ In addition, we have completed a trial of injectable naltrexone in HIV-infected heavy drinkers. We allow the

physicians flexibility with respect to choice of pharmacotherapy for a more “real world” implementation. Decisions to not offer alcohol pharmacotherapy for those with AUD will be discussed on a case by case basis with [name] or [name] in light of contraindications.⁷⁰ In addition, monthly supervision phone calls will encourage use of pharmacotherapies where appropriate. The prescribing physicians will have the final decision as to the medication, dose, and duration. Medications will be tracked through assessments and the EHR.

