MET will be provided in 4 sessions to coincide with the initial APM visits. At the first MET session with the social worker, participants will be given a personal feedback report which will provide the participants with information on their current drinking habits as well as how their drinking may affect their current health status. We will use the MET manual (based on [name] [a consultant on the current protocol] ELM Brief Intervention Study Treatment Manual) that we are using in the current **STEP** Trials that includes adaptations for HIV-infected patients. MET is grounded in research on processes of natural recovery during which patients move through stages of change – precontemplation, contemplation, determination, action, and maintenance.⁷¹ The Social Worker’s role is to assist the patient in moving through the stages of change. MET uses motivational interviewing and reflective listening to help patients identify internal sources of motivation to support reductions in alcohol. We have selected MET as a counseling platform because 1) it is consistent with the use of alcohol medications, 2) the efficacy is equivalent to other manualized therapies⁷² 3) it has applicability to a range of behavioral challenges encountered in medical settings (e.g. diet, smoking), 4) training in motivational interviewing is widely available, and 5) because it has the flexibility to address patients across a spectrum of readiness to change their alcohol use.⁷³⁻⁷⁵

Due to the declared public health emergency in March 2020, the MET and APM sessions will be done by videoconference or telephone. This will limit participants’ and employees’ exposure to COVID-19.

Training and supervision of study interventionists

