We will measure a range of pretreatment variables at baseline to ensure that participants meet eligibility criteria and that important predictor variables are measured (Table 3, Summary of Study Assessments). The baseline interview will include evaluations for alcohol, drug, and psychiatric disorders, and verify past 30-day laboratory values or collection of blood work (See Table 3). To avoid assessment reactivity,^{87,88} alcohol questions will be as brief as possible and interspersed among questions addressing other health-related domains. Using validated instruments at baseline, during treatment, and at end-of-treatment, we will examine the differential impact of CM plus stepped care on a range of measures. To minimize assessment reactivity, we will restrict assessments to those necessary and attempt to avoid those that would serve as motivation to change alcohol consumption. The primary study outcome, assessed at 6 months, was originally proportion of patients with PEth documented abstinence since this objective measure has advantages over self-report.⁸⁹ However, due to difficulty collecting PEth

during the COVID-19 pandemic, and on the recommendation of our DSMB, we changed the primary outcome to self-reported Timeline Follow Back at week 24. Abstinence confirmed by PEth was changed to a secondary outcome, Secondary study outcome, assessed at 3 months, will be proportion of patients with PEth documented abstinence. In addition, we will assess, at 6 months, alcohol consumption by TLFB and change in HIV biological markers as measured by viral load and VACS index. Exploratory analyses will evaluate the impact of CM plus stepped care on measures of medical conditions impacted by alcohol including exhaled CO, FIB-4, detectable HCV infection, depressive symptoms using the PHQ-9 and use of psychoactive medications that interact with alcohol.

Retention and Collection of Patient Locator Information

We use retention and tracking strategies developed to minimize attrition.^{90,91} We will obtain locator information on 5 individuals and update at each visit. RAs will notify patients by phone, text, mail and/or email before each assessment. We will contact other locators after 3 attempts and if unsuccessful we will send a registered letter. We couple research visits to scheduled medical visits when possible.

Study Period:

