The treatment period will be 6 months with follow up at 12 months. This will allow time for patients' treatment to be stepped up if necessary and to detect differences in alcohol consumption and biologic markers (e.g. VACS index, CD4 lymphocyte counts, and HIV viral load) that may emerge from treatment. Given the cycles of cessation and relapse to prior drinking patterns with alcohol treatment, effects may not persist.^{68,92,93} Thus, we plan follow-up assessments at 9 and 12 months. Future chronic care trials may be warranted.⁹²⁻⁹⁶

	BL	Wk 12	Wk 24	Month 9	Month 12
PEth Testing	X	X	X	X	X
Web-based Timeline Followback (TLFB) for alcohol	X	X	X	X	X
AUDIT-C	X				
NIAAA single item screen for alcohol use	X				
Gambling Disorder assessment (for eligibility)	X				
NODS (for all patients upon enrollment)	X				
VACS Index – HIV biomarkers (CD4, HIV viral load), creatinine, hemoglobin, FIB-4 components (AST, ALT, platelets), HCV serology and RNA	X	X	X	X	X
ART medication adherence by pharmacy data	X	X	X	X	X
HIV risk-taking behavior scale (HRBS)	X	X	X	X	X
Addiction Severity Index-Lite	X		X		X
ASSIT-Lite (to assess for substance use)	X	X	X	X	X
Mini-SCID alcohol (only if AUDIT-C greater than 4)	X				
Breathalyzer test (BAC) or alcohol saliva test	X	X	X	X	X
PHQ-9	X	X	X	X	X
Smoking assessment, including Fagerstrom Test for Nicotine Dependence and e-cigarette use	X	X	X	X	X
, Exhaled CO (*among people who smoke only) or urine	X	X	X	X	X

cotinine test					
Treatment Services Review	X	X	X	X	X
Urine pregnancy test, also clinically as indicated	X				
Healthcare utilization (ED visits, ID visits, hospitalization, counseling, intensive outpatient programs, detoxification)	X	X	X	X	X
Medications for alcohol and tobacco use disorder	X	X	X	X	X
Medications for depression	X	X	X	X	X
Medications for hepatitis C virus infection	X	X	X	X	X
Psychoactive medications that potentially interact with alcohol (benzodiazepines, opioids, antipsychotics, antidepressants, sleeping medications, muscle relaxants)	X	X	X	X	X
HIV History	X				
Readiness to change ruler	X				
Family history	X				
Neurocognitive assessment (TRAILS A, TRAILS B)	X	X	X	X	X
Sleep related impairment and sleep disturbance scales	X	X	X	X	X
Patient satisfaction survey		X	X	X	X

Baseline and in-treatment assessments (Table 3)

Summary of Study Assessments

Peth Testing: Self-reports of alcohol consumption will be verified using PEth biomarker which has been validated in HIV-infected and uninfected patients.^{43,97-101}

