Assessments at 9 and 12 months will include: PEth testing, pharmacy fill/refill data for ART, TLFB, VACS index, HRBS, ASI, PHQ-9, TSR, exhaled CO test or urine cotinine as indicated, HCV as indicated, past 30 day prescription of psychoactive medications that interact with alcohol. We will additionally assess measures of health care utilization (e.g. ED visits, hospitalizations, medications prescribed) based on the VA EMR or Epic. At the end of study participation all VA subjects will be offered enrollment in VACS for continued follow up.

Due to the declared public health emergency in March 2020, the assessments are done by videoconference or telephone. This will limit participants' and employees' exposure to possible COVID-19 exposure. Participants will receive \$50 upon completing the telephone assessment. We will ask participants to complete the visit when conditions permit them to come to the clinic to conduct laboratory and PEth testing.

Participant compensation for completing assessments

Participants will be compensated \$50 completing each assessment at baseline assessment, during treatment (3 months), end of treatment (6 months) and the follow-up assessment at 9 and 12-months. The total possible compensation for completing study assessments is \$250. Patients randomized to CM plus stepped care patients may earn more depending upon their response to treatment. In addition, patients randomized to CM plus stepped care will receive \$15.00 per intervention visit to cover travel costs.

1. Genetic Testing N/A

A. Describe

- i. the types of future research to be conducted using the materials, specifying if immortalization of cell lines, whole exome or genome sequencing, genome wide association studies, or animal studies are planned
- ii. the plan for the collection of material or the conditions under which material will be received
- iii. the types of information about the donor/individual contributors that will be entered into a database
- iv. the methods to uphold confidentiality

B. What are the conditions or procedures for sharing of materials and/or distributing for future research projects?

C. Is widespread sharing of materials planned?

D. When and under what conditions will materials be stripped of all identifiers?

E. Can donor-subjects withdraw their materials at any time, and/or withdraw the identifiers that connect them to their materials?

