Breathalyzer, blood/urine collections: Breathalyzer and blood and urine collections are performed primarily as safeguards and should add no risks other than those normally associated with these procedures.

Rating scales and questionnaires: Rating scales, structured interviews, and questionnaires are all non-invasive, and should also add no risks to subjects, as our past experience indicates.

Recorded sessions: Participants will be made aware during the informed consent process that sessions with the study Social Worker will be digitally recorded and that the nature of these sessions will involve participants speaking about information regarding their health status, alcohol use, HIV status, medical history, and participation in the study. However, participant names will never be recorded on the tapes and the tapes will be coded by participant number rather than name in order to protect participant confidentiality. Participants will be given the option to decline to be taped during the study.

Risks include inconvenience and concerns about confidentiality.

7. **Minimizing Risks:** Describe the manner in which the above-mentioned risks will be minimized.

Protection against risk:

As the safety of alcohol pharmacotherapy has not been established in pregnant and nursing women, they will be excluded from participation. Women of child-bearing capacity must agree to use a reliable form of birth control. Pregnant women will be referred for other alcohol treatment. Women who become pregnant during the study will be taken off study medications immediately.

NTX: Addiction Psychiatrists will be instructed to avoid prescribing NTX in patients with medical conditions that would contraindicate the use of NTX. We will instruct Addiction Psychiatrists to exclude individuals from receiving NTX if they have evidence of significant hepatocellular injury (AST, ALT > 5 times the upper limit of normal or a diagnosis of cirrhosis and Child-Pugh class greater than A or B). We will instruct Addiction Psychiatrist to monitor liver enzyme tests prior to, during, and at end of treatment and a subject whose AST or ALT rises to > 5 times the upper limit of normal will have laboratory tests repeated in one week. If liver enzymes are persistently elevated or if the individual is symptomatic, we will instruct Addiction Psychiatrists to consider discontinuing NTX and refer patients for a Hepatology evaluation.

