a. What protected health information (medical information along with the HIPAA identifiers) about subjects will be collected and used for the research?

Prior to entrance into the study, each patient will have laboratory assessments CD4 lymphocyte count, HIV viral load, creatinine, platelets, hemoglobin, AST, ALT if not obtained in the past 60 days. In addition, HCV antibody and HCV viral load (if HCV antibody positive) will be obtained if not previously documented in patient's chart. Exhaled COtest or urine cotinine will be performed among patients who have smoked at least 100 cigarettes in their lifetime and who now report smoking cigarettes every day or some days. A urine pregnancy test will be performed on female subjects and must be negative prior to beginning the study medication and will be checked monthly. In addition, we will screen patients to exclude those who have a current diagnosis or are in remission for a gambling disorder. Demographic data to be collected include age, gender, marital status, highest level education completed, employment, substance use history, duration of HIV disease, and a detailed HAART medication history. Charts will be extracted to collect health care information and service utilization information in the VA database, including labs, diagnoses, visits, medications, procedures, test results, and health care information and service utilization information in the VA database.

b. How will the research data be collected, recorded and stored?

c. How will the digital data be stored? CD DVD Flash Drive Portable Hard Drive Secured Server Laptop Computer Desktop Computer Other

d. What methods and procedures will be used to safeguard the confidentiality and security of the identifiable study data and the storage media indicated above during and after the subject's participation in the study?

The Yale Center for Medical Informatics (YCFMI) (<http://ycmi.med.yale.edu>) will be responsible for data management using a web-based clinical trial management system (CTMS). Study data will be entered into the Web-accessible CTMS. To facilitate data monitoring the CTMS will generate web accessible reports and reminders to help monitor and manage the data collection process. The system can check for data inconsistencies, omissions, and errors regularly. Data questions or problems will trigger data queries and analyses of missing data will be done periodically to assure that all forms are entered and available for analysis.

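### Section VIII requires a negative pregnancy test before study medication and monthly checks, but Table 3 schedules one test, at baseline, and otherwise leaves testing to clinical indication

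*Combined protocol and SAP*

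**What the plan says.** Two places in the combined document set out pregnancy testing.

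- **Section VIII, Protection of Research Subjects, item a:** the urine pregnancy test for female participants "must be negative prior to beginning the study medication and will be checked monthly".
- **Section V, item 3, Table 3:** the row "Urine pregnancy test, also clinically as indicated" has one mark, in the baseline column. The cells for Wk 12, Wk 24, Month 9 and Month 12 are empty.

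The following provisions bear on how the two interact.

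- **Step-up rule (Section V, item 3, APM and MET):** "Patients in the CM plus stepped care arm who have PEth > 8 ng/ml at 3 months will progress to Step 2". Section V, item 6 (Risks) confirms that the psychiatrist may prescribe alcohol medication once a patient has been stepped up after the month 3 assessment.
- **Stopping rule (Section V, item 7, Minimizing Risks):** "Women who become pregnant during the study will be taken off study medications immediately". The same section says that safety in pregnancy and nursing has not been established, and gives this as the reason for excluding those women.
- **Other safeguards:** women who do not agree to reliable birth control are excluded at entry. Prescribers are to be told not to give naltrexone to pregnant or nursing women.
- **Since March 2020:** "the MET and APM sessions will be done by videoconference or telephone". For research assessments, the Follow-up assessments section adds: "We will ask participants to complete the visit when conditions permit them to come to the clinic to conduct laboratory and PEth testing".

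**The concern.** The two places give a site different instructions for the same woman. Monthly checking cannot be squared with one scheduled test plus testing at discretion.

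The timing makes this more than a clerical mismatch. In many trials a baseline test falls just before the first dose. Here the only study-directed drug exposure begins in Step 2, about three months after baseline. The one scheduled test therefore falls well before any exposure, and none is scheduled during it.

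At stake is a participant-protection measure. The protocol itself treats exposure in pregnancy as a reason for exclusion and for immediate discontinuation, and discontinuation can follow only once a pregnancy is known. Sites working from different sections could handle the same patient differently. A site that did only what Table 3 schedules would depart from the monthly checks in Section VIII.

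**Working it through.** The plan gives no figure to reproduce. The check is a comparison of the provisions, with a count of visits and weeks.

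**1. Scheduled tests after baseline in Table 3.** The later visits are Wk 12, Wk 24, Month 9 and Month 12. Marks in the pregnancy row: 0 of 4. Neighbouring rows, such as the PHQ-9 and the Treatment Services Review, carry all five marks, so lost cells are not a likely explanation. The written list of 9- and 12-month assessments under Follow-up assessments also has no pregnancy test.

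**2. Age of the scheduled test at the earliest Step 2 prescription.** Step 2 depends on the Wk 12 PEth result.

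Wk 12 − baseline (week 0) = 12 weeks

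To this add up to 72 hours for the PEth result, if the turnaround stated for CM visits applies, and the wait for the first physician visit. About 12 weeks is thus a minimum. It applies when no as-indicated test has been done in between.

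**3. What monthly checking would amount to.** Section VIII gives neither a start nor an end, so the count depends on an assumption:

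- from the start of Step 2 (month 3) to the end of treatment (month 6): 6 − 3 = about 3 checks;
- from baseline to month 6: about 6;
- from baseline to month 12: about 12.

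On every one of these readings Table 3 schedules 0 after baseline. The conflict does not depend on the reading, but its size does.

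**4. Whether another provision closes the gap.**

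| Provision | Names a pregnancy test? | Gives a time? |
|---|---|---|
| Birth-control agreement (eligibility; Minimizing Risks) | No | At entry |
| Naltrexone instruction to prescribers (Risks; Section VI) | No | No |
| Seven APM physician tasks | No | No |
| Liver-enzyme monitoring for naltrexone and disulfiram | No (liver tests only) | Before, during and at end of treatment |
| Stopping rule on pregnancy | No | On pregnancy |

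None reconciles the two schedules.

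**5. Remote delivery.** The sessions at which drugs are prescribed moved to video or telephone. No section says how a pregnancy-test result would be obtained before a prescription made that way.

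**The case against.** Several arguments against the point have force.

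- **As-indicated testing.** The Table 3 row expressly allows it. A reader might infer that a site following Table 3 necessarily starts Step 2 drugs on a 12-week-old test, or has no means of detecting a later pregnancy. The documents do not support that, because a prescriber may test before prescribing or on suspicion. What stands is that no later test is scheduled or required by the table.
- **The words of Section VIII.** A baseline test does, literally, precede medication, so that half of the sentence can be read as met. The monthly check is the unambiguous conflict.
- **Table 3 is not a complete list of tests.** Its columns cannot show a monthly check, and it leaves out the three-weekly CM-visit tests. This explains why monthly tests are not displayed. It does not explain the empty Wk 12 and Wk 24 cells or the row label.
- **Other safeguards exist.** Contraception is required and prescribers are warned about naltrexone. It would be wrong to say that protection lapses; one safeguard, scheduled testing, is stated inconsistently.
- **The pandemic text.** A reader might infer that all laboratory work before prescribing was deferred. The deferral paragraph covers research assessments only, and the alcohol drugs are supplied through routine clinical care. What stands is narrower: the documents are silent on how the pregnancy test is done when the prescribing session is remote.
- **No effect on the statistics.** The endpoint, sample size and analysis are untouched. That is true; the point is about participant protection and uniform conduct across sites.

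**Conclusion.** The inconsistency is real, and nothing else in the documents resolves it. Section VIII requires a negative test before medication and then monthly checks. Table 3 schedules baseline only, with the rest left to clinical judgement. Under Table 3 the scheduled test is at least about 12 weeks old at the earliest prescription unless an as-indicated test intervenes, and 0 of 4 later visits carry a test to support the stopping rule.

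Its reach is limited to women of child-bearing capacity in the CM plus stepped care arm who have a PEth above the step-up threshold at 3 months and are then prescribed a medication. The documents do not state how many that is. A reader might be tempted to apply an assumed share of women to the 174 participants expected in that arm (348/2, assuming equal allocation). The documents give no such share, and the result would be only a ceiling, since not every woman is stepped up, prescribed a drug or able to become pregnant. A contrast of 12 tests with none is likewise unsupported: it assumes monthly testing from baseline to month 12, which Section VIII does not say.

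**What to change.** Reconcile the pregnancy-test row of Table 3 with Section VIII, item a, so that one testing schedule applies at all sites. The reconciled text should state:

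- when testing starts and when it stops;
- whom it covers: all female participants, or only those prescribed alcohol medication;
- how the test is done and its result obtained when APM sessions are remote.

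This review takes no position on which schedule is right; that is for the sponsor and the IRB. Whichever is chosen, the other place must be changed to match.

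The cost is an amendment to one table row and a few sentences. Any change in the number of urine tests depends on the schedule chosen.
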